8.3.3 Intermediate Visits

8.3.3.1 Visit 2

1 day (T2)

CONFIDENTIAL

This material is the property of the NYU School of Medicine and Langone Health
Do not disclose or use except as authorized in writing by the study sponsor

- Collect blood for CBD, Delta-9 THC, 11-Hydroxy Delta-9 THC, Delta-9 Carboxy THC and Anandamide levels (45 minutes post-CBD levels)
- Record adverse events as reported by participant or observed by the coordinator
- Record vital signs, results of evaluations of safety, and psychomotor effects

8.3.3.2 Visit 3

1 week (T3)

- Collect urine for urine drug analysis and urine pregnancy test
- Collect blood for CBD, Delta-9 THC, 11-Hydroxy Delta-9 THC, Delta-9 Carboxy THC and Anandamide levels (pre-CBD and 45 minutes post-CBD levels)
- Record adverse events as reported by participant or observed by investigator
- Record vital signs, results of evaluations of safety, psychomotor/subjective effects, cognitive function, AUD-related domains and drinking
- Provide additional medication to the participant according to the study's MOP requirements
- Record participant's adherence to treatment program

8.3.3.3 Visit 4

4 weeks (T4)

- Collect urine for urine drug analysis and urine pregnancy test
- Collect blood for CBD, Delta-9 THC, 11-Hydroxy Delta-9 THC, Delta-9 Carboxy THC and Anandamide levels (pre-CBD and 45 minutes post-CBD levels), LFTs
- Collect blood for CDT levels
- Record adverse events as reported by participant or observed by investigator
- Record vital signs, results of evaluations of safety, psychomotor/subjective effects, AUD-related domains, and drinking
- Provide additional medication to the participant according to the study's MOP requirements
- Record participant's adherence to treatment program

8.3.3.4 Visit 5

4 weeks + 1 day (T5)

- Collect blood for CBD, Delta-9 THC, 11-Hydroxy Delta-9 THC, Delta-9 Carboxy THC and Anandamide levels (45 minutes post-CBD levels)
- Record adverse events as reported by participant or observed by coordinator
- Record vital signs, results of evaluations of safety, psychomotor/subjective effects

8.3.3.5 Visit 6

5 weeks (T6)

- Collect urine for urine drug analysis and urine pregnancy test
- Collect blood for CBD, Delta-9 THC, 11-Hydroxy Delta-9 THC, Delta-9 Carboxy THC and Anandamide levels (pre-CBD and 45 minutes post-CBD levels)
- Record adverse events as reported by participant or observed by investigator.
- Record vital signs, results of evaluations of safety, psychomotor/subjective effects, cognitive function, AUD-related domains, cue/stress response task, and drinking
- Provide additional medication to the participant according to the study's MOP requirements
- Record participant's adherence to treatment program

8.3.3.6 Visit 7

8 weeks (T7)

- Collect urine for urine drug analysis and urine pregnancy test
- Collect blood for CBD, Delta-9 THC, 11-Hydroxy Delta-9 THC, Delta-9 Carboxy THC and Anandamide levels (pre-CBD and 45 minutes post-CBD levels), LFTs
- Collect blood for CDT levels
- Record adverse events as reported by participant or observed by investigator

CONFIDENTIAL

This material is the property of the NYU School of Medicine and Langone Health
Do not disclose or use except as authorized in writing by the study sponsor

- Record vital signs, results of evaluations of safety, psychomotor/subjective effects, AUD-related domains, and drinking
- Provide additional medication to the participant according to the study's MOP requirements
- Record participant's adherence to treatment program

8.3.3.7 Visit 8

9 weeks (T8)

- Collect urine for urine drug analysis and urine pregnancy test
- Collect blood for CBD, Delta-9 THC, 11-Hydroxy Delta-9 THC, Delta-9 Carboxy THC and Anandamide levels (pre-CBD levels), LFTs
- Record adverse events as reported by participant or observed by coordinator
- Record vital signs, results of evaluations of safety, psychomotor/subjective effects, AUD-related domains, and drinking

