6.6.2 Handling of Participant Withdrawals or Termination

Every effort will be made to undertake the protocol-specified safety follow-up procedures to capture AEs, SAEs, and UPs. The investigator will attempt to obtain at a minimum survival data on all participants lost to follow-up. If a participant is lost to follow-up, the study team will attempt to contact the participant 3 times by telephone and twice by email. If the participant fails to respond, locators identified by the participant at screening will be contacted in the method specified by the participant. If participants withdraw, are terminated, or are lost to follow-up prior to the end of the 8-week treatment phase (prior to T7), they will not be replaced to allow for 40 participants to complete the 8-week treatment phase (through T7), and their partial data will be handled according to the statistical analysis plan (SAP).

CONFIDENTIAL

This material is the property of the NYU School of Medicine and Langone Health
Do not disclose or use except as authorized in writing by the study sponsor

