7.1.7 Starting Dose and Dose Escalation Schedule

All participants will receive 600mg/day CBD vs. Placebo for weeks 1-4 of treatment, unless contraindicated, and will be escalated to 1200mg/day CBD vs. Placebo for weeks 5-8 of treatment, unless contraindicated.

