7.1.9 Duration of Therapy

The duration of the active treatment portion of the study is 8 weeks, followed by an additional 4-week follow-up period. In order for participants to be included in the primary statistical analyses, they must complete the 8-week treatment phase of the study (through T7).

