7.3.1 Administration of Intervention

CBD (or placebo) will be administered daily for 8 weeks. The first administration of each dose of CBD vs. placebo (at T1 and T4) will take place at the study site. Participants will remain at the study site with a study team member for approximately 2 hours following the initial administration of each dose of CBD, and participants will not be permitted to leave the study site until they are able to pass a standard field sobriety test (a walk-and-turn task, one-leg stand, Romberg's test, finger-finger test, and counting backwards [97]). If there are no AEs during this time period or lasting intoxicating effects of the study drug (i.e. participants are able to pass field sobriety tests 2-3 hours after study drug administration), participants will be dispensed the proper quantity of study drug (CBD or placebo) to self-administer daily at home until the next scheduled study visit (i.e. a 1- or 3-week supply, depending on the visit).

CONFIDENTIAL

This material is the property of the NYU School of Medicine and Langone Health
Do not disclose or use except as authorized in writing by the study sponsor

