Alcohol Abstinence Self-efficacy "P"		✓				✓					
Short Inventory Of Problems "P"		✓				✓					
Penn Alcohol Craving Scale "P"		✓				✓					
Self-compassion Short Form "P"		✓				✓					
Beck Anxiety Inventory		✓				✓					
Beck Depression Inventory		✓				✓					
C-SSRS		✓				✓					
PTSD-Related Domains											
THQ		✓									
CTQ		✓									
PCL-5											
Cue/Stress Script Interview											
Imagery Scripts			✓								
Cue/Stress Task								✓			

CONFIDENTIAL

This material is the property of the NYU School of Medicine and Langone Health
Do not disclose or use except as authorized in writing by the study sponsor

Script Randomization					✓			
Alcohol Script Pre-Imagery *Pt					✓			
Alcohol Script Imagery *Pt					✓			
Alcohol Script Recovery *Pt					✓			
Neutral Script Pre-Imagery *Pt					✓			
Neutral Script Imagery *Pt					✓			
Neutral Script Recovery *Pt					✓			
Stress Script Pre-Imagery *Pt					✓			
Stress Script Imagery *Pt					✓			
Stress Script Recovery *Pt					✓			
Differential Emotions Scale IV *Pt					✓			
Physiological Stress Response Results					✓			
Alcohol Use								*
Follow Up Timeline Followback		✓		✓	✓	✓	✓	✓
Medication/Clerical								**
Research Visit Form	✓	✓	✓		✓	✓	✓	✓
Menstrual Calendar	✓	✓	✓		✓	✓	✓	
Medication Dispensing	✓		✓		✓	✓	✓	
Medication Compliance *Pt*			✓		✓	✓	✓	
Medication Management	✓		✓		✓	✓	✓	
Participant Treatment Assignment Guess *Pt*							✓	
Study Medication Questionnaire *Pt*							✓	
Treatment Satisfaction *Pt*							✓	
Unscheduled Forms								
Study Termination Form								
Consent Withdrawal								
Contact Attempts								

* should we do a separate phone form?
** medication management session documentation? Or just a question in dispensing form

8 Study Procedures and Schedule

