21.3.5 Adherence and Retention Analyses

Adherence to the protocol will be assessed with a smartphone-assisted medication adherence platform [119] in which the subject takes a video of drug administration at each dose, and transmits this to study personnel. This program has been used successfully in previous studies, and includes security provisions that ensure protection of confidentiality and privacy. Circulating concentrations of CBD will also be collected at T1-T8 to verify treatment adherence.

Number of participants that complete the treatment phase of the study (through T8), complete the follow-up phase of the study (through T9), and are lost to follow-up will be collected. Frequency of and reasons for discontinuation of the intervention or study follow-up will also be tallied.

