21.4 Sample Size

We will enroll approximately 60 participants, and randomize approximately 40 participants to meet our recruitment goal (through week 8/T7). Sensitivity to detect effects with the proposed study design was calculated for each hypothesis at power = 0.95 for univariate outcomes with 40 participants in 2 groups at alpha = 0.05 for the analyses described above. Hypotheses 1a and 1c are powered to detect effect sizes of approximately $d = 0.2$. Hypotheses 2a and 2b are powered to detect effect sizes of $d = 0.2$ and $d = 0.3$, respectively. Hypothesis E (exploratory hypothesis) is powered to detect an effect size of $d = 0.6$, therefore we are only powered to detect substantial impacts on drinking outcomes for this exploratory aim.

22 Source Documents and Access to Source Data/Documents

Source data is all information, original records of clinical findings, observations, or other activities in a clinical trial necessary for the reconstruction and evaluation of the trial. Source data are contained in source documents. Examples of these original documents, and data records include: hospital records, clinical and office charts, laboratory notes, memoranda, subjects' diaries or evaluation checklists, study medication dispensing records, recorded data from automated instruments, copies or transcriptions certified after verification as being accurate and complete, microfiches, photographic negatives, microfilm or magnetic media, x-rays, subject files, and records kept at the dispensation site, at the laboratories, and at medico-technical departments involved in the clinical trial. It is acceptable to use CRFs as source documents. If this is the case, it should be stated in this section what data will be collected on CRFs and what data will be collected from other sources.

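### Section 21.3.5 counts treatment completion through T8 (week 9), although the 8-week treatment phase ends at T7; the T7 medication line should also be clarified

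*Combined protocol and SAP*

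**What the plan says.** **End of treatment.** Section 7.1.9 gives 8 weeks of active treatment followed by 4 weeks of follow-up. To enter the primary analyses, participants are told "they must complete the 8-week treatment phase of the study (through T7". Section 6.6.2 deals with people who withdraw or are "lost to follow-up prior to the end of the 8-week treatment phase (prior to T7". Section 21.4 sets the number randomized "to meet our recruitment goal (through week 8/T7". The Rationale (3.3) places the last two assessments 1 and 4 weeks after treatment stops, which are T8 and T9.

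**Completion count.** Section 21.3.5 will report the "Number of participants that complete the treatment phase of the study (through T8", then the number completing follow-up through T9, then those lost to follow-up.

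**Supply.** Section 7.3.1 has participants given enough drug "to self-administer daily at home until the next scheduled study visit (i.e. a 1- or 3-week supply, depending on the visit". Section 7.1.7 states that participants "will be escalated to 1200mg/day CBD vs. Placebo for weeks 5-8 of treatment, unless contraindicated"; no dose is defined after week 8. The visit lists carry a supply line at T1, T3, T4, T6 and T7. From T3 on it reads "Provide additional medication to the participant according to the study's MOP requirements". The T7 list also requires blood before and 45 minutes after a dose.

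**The concern.** The completion count and the analysis population use different visits for the same event. Section 7.1.9 makes completion through T7 the condition for entering the primary analyses, while 21.3.5 counts completion one visit later, in what 7.1.9 calls follow-up. The reported number of treatment completers could therefore be smaller than the number who qualified for the primary analyses by completing treatment. Feasibility is among the study's stated purposes (5.1), so the completion rate is a result in its own right.

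The T7 medication line raises a related question about when drug stops. At T3, T4 and T6 the same wording covers a take-home pack. Were T7 handled in the same way, dosing would run to week 9. The week-9 liver test, the only one of the four (screening, weeks 4, 8 and 9) placed after treatment, would then be taken on drug. The first week of the post-treatment drinking window in 21.3.10 would also be on drug.

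**Working it through.** **1. Where treatment ends**

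| Section | Visit used |
|---|---|
| 6.6.2 | T7 |
| 7.1.9 | T7 |
| 21.4 | week 8 / T7 |
| 3.3 | T8 is 1 week after treatment stops |
| 21.3.5 | T8 |

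Four sections agree on week 8. Only 21.3.5 differs.

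**2. Effect on the count.** With about 40 randomized 1:1, one participant who attends T7 and misses T8 changes the completion rate by:
- overall: 1/40 = 2.5 percentage points;
- within an arm of about 20: 1/20 = 5 percentage points.

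The documents do not say how many such participants to expect. With none, the two definitions give the same count.

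**3. Supply before T7.** Take the weeks from each dispensing visit to the next. T2 and T5 have no supply line in their visit lists.
- T1 to T3: 1 week
- T3 to T4: 3 weeks
- T4 to T6: 1 week
- T6 to T7: 3 weeks

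The sum is 1 + 3 + 1 + 3 = 8 weeks. This reproduces the stated treatment duration, and every interval is a 1- or 3-week supply as 7.3.1 says. In capsules: 28 × 3 + 28 × 6 = 252. In dose: 28 × 600 + 28 × 1200 = 50,400 mg. No take-home supply is due at T7.

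**4. What the T7 line could mean**
- *A pack to T8* (an assumption, since no quantity is given): 7 × 6 = 42 capsules = 8,400 mg; 8,400/50,400 = 16.7% extra exposure at full dose; 7 of 28 follow-up days (25%) on drug.
- *One on-site morning dose*: 3 × 200 = 600 mg; 600/50,400 = 1.2%; no ninth week.
- *Nothing issued*: no effect.

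**5. Why the on-site dose must remain possible.** No visit windows are given, so assume T1 = day 1 and T6 = day 36. The T6 pack is 21 × 6 = 126 capsules.
- T7 on day 57, with on-site doses counted within the packs: the pack ends on day 56 and the T7 dose needs 3 more capsules.
- T7 on day 56: 20 × 6 = 120 capsules are used by day 55 and 6 remain.

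The T7 line may therefore be needed under one day convention and unnecessary under the other.

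**The case against.** The strongest reply concerns the T7 line. It gives no quantity, does not mention home use, and defers to a manual of procedures that is not among the documents. A dose must be taken that day for the 45-minute sample, and on the day-57 convention the capsules for it have to come from somewhere. The 8-week limit is stated repeatedly, including at the start of 7.3.1 itself, so its next-visit rule cannot sensibly extend treatment. Section 7.2 already requires unused drug to be returned. This stands: the line is unclear, but it is not shown to be wrong.

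A reader might infer that the protocol prescribes a ninth week of drug, or that the week-9 liver test is taken on treatment. The documents support neither. Nor does the "Medication Dispensing" row of the schedule settle it. The row shows five ticks where the supply sum needs four visits, but its columns are broken in the text available, so no tick can be assigned to T7. Even if a pack had been issued in error, T8 also draws blood for CBD levels, and adverse events are followed to resolution or stabilization with laboratory tests as needed.

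On 21.3.5, it can be said that the tally is descriptive, that 7.1.9 separately and clearly fixes who enters the primary analyses, and that completion through T7 can be counted from visit records. All true. It limits the consequence but does not make the stated rule right: followed literally, 21.3.5 misreports completion of an 8-week phase.

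**Conclusion.** Section 21.3.5 is wrong as written, and this can be said with high confidence. It conflicts with three sections that use T7 and with the Rationale, which places T8 after treatment has stopped. The size is 2.5 points on the overall completion rate per participant who attends T7 but misses T8, assuming 40 randomized; how many there will be is unknown. The primary-analysis rule in 7.1.9, the CBD levels through T7, and the power and alpha figures are unaffected, so it would be wrong to infer that the primary analysis set itself is misdefined.

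The T7 medication line is a secondary point, and only an ambiguity. The 42 capsules, the 16.7% extra exposure, the on-drug week-9 liver test and the 25% of follow-up days all depend on a T7-to-T8 pack having been issued. If T7 supplied only the on-site dose, or nothing, none of these arises.

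**What to change.** 1. In 21.3.5, change T8 to T7 in the definition of treatment-phase completion. This is a one-word edit with no cost.
2. In 8.3.3.6, replace the supply bullet with: *No take-home medication is dispensed. Any medication provided at this visit is only the dose taken on site for the 45-minute sample. Collect unused medication.* Leave the exact last dose to the study's visit-day convention, because fixing it at the T7 morning dose would drop an evening dose if T7 falls on day 56.
3. Check that the manual of procedures and the dispensing row of the schedule agree with this at T7.
4. Check the Study Drug Dispensation Log described in 7.2. If it shows take-home drug issued at T7, identify those participants when reporting week-9 liver tests and the T8-T9 drinking data.

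Items 2 to 4 cost one line of text and a review of existing records. No visit, sample or data item is added, and the week-8 post-dose sample is kept.

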8.3.4 Final Telephone Follow-Up

12 weeks (T9)

- Record adverse events as reported by participant
- Record drinking

8.3.5 Unscheduled Visit

Unscheduled visits will be documented on an unscheduled visit form.

8.4 Concomitant Medications, Treatments, and Procedures

All concomitant prescription medications taken during study participation will be recorded on the case report forms (CRFs). For this protocol, a prescription medication is defined as a medication that can be prescribed only by a properly authorized/licensed clinician. Medications to be reported in the CRF are concomitant prescription medications, over-the-counter medications and non-prescription medications.

8.5 Prohibited Medications, Treatments, and Procedures

Treatment with medications including cannabinoids; treatments for addictions including alcohol; moderate to strong inhibitors of CYP3A4 or CYP2C19; medications metabolized primarily by CYP3A4, CYP3A5, or CYP3A7; and medications with a narrow therapeutic index which are substrates of UGT1A9, UGT2B7, CYP2C8, CYP2C9, CYP2C19, CYP1A2, or CYP2B6 will not be permitted unless discussed with and approved by the PI.

9 Definitions of Key Terms

An adverse event (AE; also referred to as an adverse experience) is any untoward medical occurrence associated with the use of a drug (pharmaceutical investigational product) in humans, which does not necessarily have a causal relationship with that treatment. An AE can therefore be any unfavorable and unintended sign (e.g., an abnormal laboratory finding or test result), symptom, disease, accident, or worsening (increase in severity or frequency) of a pre-existing abnormality, temporally associated with the use of the drug, whether or not considered related to the drug. An AE can arise from any use of the drug (e.g., off-label use, use in combination with another drug and from any route of administration, formulation, or dose, including overdose).

A serious adverse event (SAE) is an adverse drug or biologic or device experience occurring during any study phase (i.e., screening, admission, treatment, or follow-up), and at any dose of the study drug, comparator or placebo, that results in one or more of the following criteria:

- Results in death
- Is life-threatening*
- Requires in-patient hospitalization (i.e., admission) or prolongation of existing hospitalization

CONFIDENTIAL

This material is the property of the NYU School of Medicine and Langone Health
Do not disclose or use except as authorized in writing by the study sponsor

- Results in persistent or significant disability** or incapacity
- Is a congenital abnormality or birth defect (in an offspring)
- Is an important medical event that may not result in death, be life-threatening, or require or prolong hospitalization may be considered an SAE when, based upon appropriate medical judgment, the event may jeopardize the subject or may require medical or surgical intervention to prevent one of the outcomes listed above. Examples of important medical events include events requiring intensive treatment in an emergency department, convulsions that do not require in-patient hospitalization, or the development of drug dependency or drug abuse (see Section 8, Other Significant Adverse Events).

***Life-threatening:** Any AE that places the subject, in the view of the investigator, at immediate risk of death from the reaction as it occurred; it does not include a reaction that, had it occurred in a more severe form, might have caused death.

****Disability:** A substantial disruption of a person's ability to conduct normal life functions.

10 Specification of Safety Variables

Safety and toxicity monitoring will be performed throughout the study for all subjects. Safety variables to be assessed include AEs, vital signs, and safety laboratory values, when collected.

The occurrence of an AE or SAE may come to the attention of study personnel during study visits and interviews of a study participant presenting for medical care, or upon review by a study monitor. At each study visit following screening, designated study team members will inquire about the occurrence of AE/SAEs since the last visit.

11 General Guidelines

All AEs, regardless of causality or severity, must be immediately recorded on the AE CRF when volunteered by the subject or solicited through a study assessment questionnaire. The CRC will record all AEs, regardless of causality or severity, with start dates occurring any time after informed consent is obtained until 7 (for AEs) or 30 (for SAEs) days after the last day of study participation on the AE case report forms (CRF). Information to be collected includes event description, time of onset, clinician's assessment of severity, relationship to study product (assessed only by those with the training and authority to make a diagnosis), and time of resolution/stabilization of the event.

Any medical condition that is present at the time that the participant is screened will be considered as baseline and not reported as an AE. However, if the study participant's condition deteriorates at any time during the study, it will be recorded as an AE.

Changes in the severity of an AE will be documented to allow an assessment of the duration of the event at each level of severity to be performed. AEs characterized as intermittent require documentation of onset and duration of each episode.

At the last scheduled visit, the CRC should instruct each subject to report any subsequent event(s) that the subject, or the subject's personal physician, believes might reasonably be related to participation in this study.

